## **Background and Rationale for Study**

Functional use of the upper limb during tasks requires coordination of joints of the upper extremity (van Andel, Wolterbeek, Doorenbosch, Veeger, & Harlaar, 2008). Persons with central nervous system (CNS) dysfunction often have difficulty incorporating their affected limb effectively and efficiently into functional activities due to muscle weakness and/or spasticity (Gillen, 2011). Poor functional use of the affected limb and/or motor recovery may lead to development of learned nonuse of the affected limb (Taub, Uswatte, & Pidikiti, 1999), compensatory movement patterns (Mackey, Walt, & Stott, 2006) as well as muscle or joint contracture (Milazzo & Gillen, 2011). This may further interfere with their occupational performance and restrict life roles.

Traditional rehabilitation interventions emphasize motor training on the reduction of spasticity (Gillen, 2011). However, active movement and muscle strength of forearm supination are found strongly associated with motor function recovery, rather than spasticity (Braendvik, Elvrum, Vereijken, & Roeleveld, 2010; O'Dwyer, Ada, & Neilson, 1996). In contrast, task-oriented functional training trials, such as the occupational therapy (OT) task-oriented approach (Almhdawi, 2011; Flinn, 1995) and the Constraint-Induced Movement Therapy (Page, Levine, & Leonard, 2005; Page, Levine, Leonard, Szaflarski, & Kissela, 2008; Taub, Uswatte, & Elbert, 2002; Taub et al., 2006; Wolf et al., 2008), have demonstrated promising evidence that persons with CNS dysfunction benefit from the training in improvement of increase functional use and motor function of the affected limb. However, the role of forearm movements is not addressed in rehabilitation interventions literature.

Occupational therapists often employ orthotic interventions for persons with CNS dysfunction (Milazzo & Gillen, 2011; Watanabe, 2004). Most orthotic designs are static and aimed at the wrist and/or hand with purposes of spasticity reduction, correction or prevention of deformity (Milazzo & Gillen, 2011). However, the effects remain controversial (Lannin & Herbert, 2003). Given that static orthoses may interfere with functional performance and may further develop muscle or joint contracture, compensatory movements or learned nonuse of the affected limb (Mell, Childress, & Hughes, 2005; Milazzo & Gillen, 2011), a dynamic or mobilization orthosis can be considered to assist or enhance functional use of the affected limb during functional tasks (Dunning et al., 2008; Farrell, Hoffman, Snyder, Guiliani, & Bohannon, 2007; Hoffman & Blakey, 2011; Lannin & Ada, 2011; Pitts & O'Brien, 2008). However, research evidence regarding the effects of an orthosis that assists forearm movements for this population found in the literature is limited.

The proposed research project will use a randomized clinical trial to investigate the efficacy of a forearm rotation orthosis combined with the OT task-oriented approach for persons with a hemiparetic arm on functional performance, motor function, and range of motion. We expect that the results would significantly improve participants' functional performance and motor function as well as prevent or reduce secondary complications due to CNS dysfunction. The results may also benefit the rehabilitation professions in developing treatment protocols for this population.

## Methodology

### Study design

This study will employ a randomized, single-blinded, two-group, repeated measure design (Table 1).

Table 1. *Experimental design of the internal pilot study*

Group/Week			Week 1	Week 2-7	Week 8	Week 9-14	Week 15
M	R	A	O1	Orthosis	O2	Orthosis+OTTO	O3
M	R	B	O1	No treatment	O2	OTTO	O3

*Note.* M = matching with severity of motor function of the upper extremity; R = random assignment; O1,2,3 = time points for outcomes measures; Orthosis = six weeks of forearm rotation-assist orthotic intervention; OTTO = six weeks of OT task-oriented approach intervention.

### Objectives

The primary purpose of this study is to investigate the efficacy of a forearm rotation orthosis combined with the OT task-oriented approach for persons with a hemiparetic arm. Hypotheses of this study are that 1) participants who wear the forearm rotation orthosis will demonstrate significantly greater improvement in functional performance and active range of motion of forearm rotators compared to those who do not; 2) all participants who receive the OT task-oriented approach intervention will demonstrate significant improvement in functional performance; and 3) all participants who receive the OT task-oriented approach intervention will demonstrate significant improvement in motor function of the upper extremity.

### Study endpoints

The primary endpoint is the functional improvement. “Functional improvement” represents improvement in the performance of everyday activities. The secondary endpoints are active range of motion and muscle strength, including grip and pinch, of the involved upper extremity as well as orthosis compliance.

Outcome measures for the primary endpoint include the *Canadian Occupational Performance Measure* (COPM) for self-perceived functional performance and satisfaction with performance, the *Wolf Motor Function Test* (WMFT) for quantitatively measuring the motor function of the upper extremity, and the *Motor Activity Log* (MAL) for measuring participants’ actual use of the involved arm in the real world.

Outcome measures used for the secondary endpoints include goniometric measurements for active and passive range of motion (ROM), hand-held dynamometry and manual muscle testing for muscle strength of the upper extremity, Jamar Dynamometer for grip strength, pinch gauge for pinch strength, as well as information collected by the Nike+ FuelBand regarding numbers of hours they wear the orthosis everyday throughout the study period for adherence with the orthosis.

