### **Treatment allocation**

Participants who are eligible and willing to participate in this study will first be matched with the severity of the motor function of the involved upper extremity measured by the upper extremity subscale of the Short Form Fugl-Meyer Motor Function Assessment. Participants will be classified as mild, moderate, and severe groups. Participants in each group will then be randomized in a 1:1 allocation ratio to either the Group A or B (Figure 1). The primary investigator, [name], will randomly assign eligible participants at the screening session using sealed envelopes with an equal number of both intervention

conditions to balance group size (10 for each matched group with 5 Group As and 5 Group Bs).

[figure not shown]

Figure 1. Study schematic for treatment allocation.

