### **Sample size estimation**

We plan to enroll 30 participants in the study. Based on anticipated number of screen failures and/or withdrawals, the maximum number of participants whom we will consent in order to achieve the scientific objectives of this study is 40. Note that the number of participants described above is a rough estimate of the sample size needed, since there is no evidence to address the primary question of interest. This proposed project involves pilot/preliminary investigation, which will be used to calculate the effect sizes that need to be used for the future study.

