## Study plan

**Intervention.** Participants in the Group A will experience the orthotic intervention followed by the orthosis plus OT task-oriented approach intervention. Participants in the Group B will first undergo a period of no treatment followed by the OT task-oriented approach only (Figure 3).

[figure not shown]

Figure 3. Flowchart for the proposed protocol.

**Use of the Nike + FuelBand as monitor and placebo.** The Nike+ FuelBand will serve as a monitor for all participants throughout their study period. The FuelBand is a commercially available wristband designed to measure activities throughout a day. The

Orthosis for stroke  
Protocol Number: 1309M42881

wristband is available in three sizes. Researcher will adjust the length for each participant, by removing 8mm link or adding up to 16mm to each wristband.

All participants will wear the Nike+ FuelBand at the wrist level throughout the study period and will be informed that the wristband is used to monitor their use of the arms during a day. Participants experiencing the orthotic intervention (Group A) will wear the forearm rotation orthosis on top of this wristband. All participants will receive weekly phone calls from the investigator reminding them to recharge the wristband because the wristband needs to be recharged by connecting to a computer or any device with USB port every 4-7 days.

Conditions involving OT task-oriented approach intervention consists of 18 hours of intervention time (three one-hour or two 1.5-hour session per week) of functional and motor training. Each session will concentrate on how to engage the affected arm actively, effectively, and efficiently in functional tasks that are meaningful to the participant. Suggested evaluation and intervention procedures for the OT task-oriented approach are illustrated in Figure 4 and 5.

[figure not shown]

Figure 4. Flowchart for suggested evaluation procedure for OT task-oriented approach.

Copied from Almhawi (2011) with permission.

[figure not shown]

Figure 5. Flowchart for suggest treatment for OT task-oriented approach. Copied from Almhawi (2011) with permission.

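### Orthosis hours are to be taken from an activity band worn whether or not the orthosis is on, so band data alone cannot give them

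*Combined protocol and SAP*

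**What the plan says.** Under Study endpoints, orthosis compliance is a secondary endpoint, and its only stated source is "information collected by the Nike+ FuelBand regarding numbers of hours they wear the orthosis everyday".

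The Study plan, in the paragraphs on the FuelBand as monitor and placebo, describes the band as a commercial device for measuring daily activity. It states that "All participants will wear the Nike+ FuelBand at the wrist level throughout the study period", and that participants "will be informed that the wristband is used to monitor their use of the arms during a day". Group A puts the orthosis on over the band. Group B is never assigned an orthosis: "Participants in the Group B will first undergo a period of no treatment followed by the OT task-oriented approach only".

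The orthosis paragraph of the Study plan asks Group A to wear the orthosis during functional tasks in the orthosis-only phase, to wear it at research visits in the next phase with encouragement to continue elsewhere, and to leave it off at evaluation sessions. It also plans three bi-weekly calls to support adherence. The FuelBand paragraphs plan a different set: "All participants will receive weekly phone calls from the investigator reminding them to recharge the wristband".

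Data analysis provides for a descriptive summary of adherence and gives no rule for deriving it.

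**The concern.** The instrument named for the endpoint does not, as described, measure the endpoint. It records activity at the wrist, while the quantity wanted is the time a second item was worn on top of it. If the plan is followed as it stands, band data would be reported as hours of orthosis wear.

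Adherence matters for interpretation here. Hypothesis 1 concerns participants who wear the orthosis, wear in weeks 2-7 takes place largely in the participant's own setting, and the study is meant to supply effect sizes for a later one (Sample size estimation). If the orthosis effect is small or absent, the reader will want to know whether the orthosis was worn. Band data alone would not tell them.

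**Working it through.** The plan states no figure for wear hours, so there is none to reproduce. The check sets the sections side by side and then counts the contacts that could carry a wear record.

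**Can band data yield orthosis hours?**

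- Quantity wanted (Study endpoints): orthosis hours per day, H.
- What the band is said to measure (Study plan): activity during the day. No detection of the orthosis is described.
- When the band is on: throughout, in both groups. Call its recorded hours T.
- When the orthosis is on: in Group A only, over the band, and intermittently in weeks 2-7.
- The instructions to remove or stop using the orthosis (Potential risk of the orthosis; Appendix A) do not address the band. They ask the participant to report the problem, but no visible text carries that report into the adherence measure.

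If the band is on whenever the orthosis is, as the plan asks, all that follows is 0 ≤ H ≤ T. Nothing visible narrows that range: there is no log, orthosis sensor, on/off marker or conversion rule. Group B shows the lower end, with H = 0 by design while the band is worn throughout. The same gap exists within Group A without any reference to Group B.

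**Which planned contacts could record wear in Group A?**

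- Group A size: Treatment allocation gives "10 for each matched group with 5 Group As and 5 Group Bs", and there are three severity groups, so 3 × 5 = 15. Both arms together give 30, matching "We plan to enroll 30 participants in the study".
- Phase lengths (Table 1): weeks 2-7 and weeks 9-14 are 6 weeks each, in line with "Orthosis = six weeks of forearm rotation-assist orthotic intervention".
- Calls in weeks 2-7: 3 if only the bi-weekly calls count (6 × 7 / 3 = 14 days apart); 6 if only the weekly calls count (7 days apart); 3 + 6 = 9 if both are made.
- Visits for the OT task-oriented approach (OTTO) in weeks 9-14: 2 × 6 = 12 or 3 × 6 = 18, on average 7/2 = 3.5 or 7/3 = 2.3 days apart. Both schedules reproduce the plan's 18 treatment hours (12 × 1.5 and 18 × 1).
- Weekly calls in weeks 9-14: 0 or 6. The weekly calls carry no stated phase limit.
- Entries per participant: minimum 3 + 12 = 15; maximum 9 + 18 + 6 = 33.
- Entries in all: 15 × 15 = 225 to 15 × 33 = 495, excluding week 8.

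The minimum treats the weekly calls as not counted.

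**The case against.** The strongest reply is that adherence is a secondary, descriptive measure in a pilot study, and that the investigator has regular contact with Group A and would learn of non-wear. The first part stands and limits the consequence. The second does not resolve the point: the calls are described as reminders and adherence support, no recording of wear time is mentioned, and the endpoint definition still names the band.

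A second reply is that a log may exist in material not available here. That is possible. Even so, the Study endpoints text names the band as the source of hours and would need correcting.

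Three stronger readings might be inferred, and the documents do not support them.

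- That half the adherence data are wrong, because 15 of 30 participants wear the band without an orthosis. The 50% only restates 1:1 allocation. Group B has no orthosis to adhere to, so the figure measures no error in Group A's adherence.
- That a participant who abandons the orthosis would produce exactly the same band record as one who wears it. The documents do not say what the band records under an orthosis, or whether activity would differ. What can be said is that no rule is given for telling the two apart.
- That the efficacy comparisons are compromised. COPM, WMFT, MAL, range of motion and strength do not depend on the band.

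**Conclusion.** The point holds as a mismatch between a named endpoint and its stated source. As described, the band record does not determine orthosis hours, and nothing visible supplies the missing link. The size of the error in hours per day cannot be computed, because the documents give no wear hours and no account of what the band registers with the orthosis on.

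The consequence is limited to the adherence summary and to any reading of the orthosis effect against actual wear. It should be corrected because the correction is cheap and unrecorded wear is hard to recover afterwards, not because the randomised comparisons are at risk.

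The conclusion rests on the visible text of the endpoint, intervention, analysis and Appendix A sections. A wear log in a figure or consent page would reduce the practical problem but would leave the endpoint definition to be amended.

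**What to change.** - **Study endpoints:** stop using FuelBand output as the source of orthosis hours and describe it as activity data only. Do not compare it between groups unless the band is on the affected wrist in both. The plan puts it on the affected arm in Group A but does not state the wrist for Group B.
- **Definition:** adherence is Group A's reported orthosis hours per day. At planned calls and OTTO visits, record the days worn since the last contact and the usual hours on those days. Then hours per day = days worn × usual hours / days covered. A brief daily log for Group A is an alternative that shortens recall.
- **Weeks 9-14:** also record whether the orthosis was worn at each treatment visit, which can be observed directly.
- **Handling:** keep these records from the blinded evaluators.
- **Data analysis:** summarise weeks 2-7 and weeks 9-14 separately, report the days covered, and do not fill in uncovered days. State whether week 8 counts, since the endpoint text covers the whole study period while the orthosis paragraph excludes wear only at evaluation sessions.
- **Calls:** reconcile the weekly calls with the three bi-weekly calls, since this sets the recall period.

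The cost is wording changes in Study endpoints, the FuelBand and orthosis paragraphs of the Study plan, and Data analysis, plus the 15 to 33 short entries per Group A participant counted above. Nothing is added for Group B.

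The downsides should be stated in the plan. Participants would be reporting to the investigator who makes the adherence calls and treats most of them, which may overstate wear. Recall in weeks 2-7 may run to 7 or 14 days, and asking may itself prompt wear slightly.

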### **Treatment allocation**

Participants who are eligible and willing to participate in this study will first be matched with the severity of the motor function of the involved upper extremity measured by the upper extremity subscale of the Short Form Fugl-Meyer Motor Function Assessment. Participants will be classified as mild, moderate, and severe groups. Participants in each group will then be randomized in a 1:1 allocation ratio to either the Group A or B (Figure 1). The primary investigator, [name], will randomly assign eligible participants at the screening session using sealed envelopes with an equal number of both intervention

conditions to balance group size (10 for each matched group with 5 Group As and 5 Group Bs).

[figure not shown]

Figure 1. Study schematic for treatment allocation.

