### **Participant selection**

The target population for this study is stroke patients who have a hemiparetic arm. Subjects will be recruited from a) local hospitals and institutions in the Twin Cities metro area, including advertising at Fairview hospitals and the stroke center at the North Memorial Hospital and b) the Onsite clinic at the University of Puget Sound at which the PI was a graduate from the occupational therapy program.

Inclusive criteria in this study include:

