**Data collection plan and schedule.** The timing of screening, randomization, and follow-up visits are illustrated in Figure 2. The primary investigator will screen potential participants' eligibility using the Mini-Mental Status Examination (MMSE), the Short Form Fugl-Meyer (S-FM), and ROM. There will be three time points for data collection (pretest, posttest 1, and posttest 2). Trained occupational therapy students recruited from the University of Minnesota and University of Puget Sound will serve as the blinded evaluators to implement all assessments except the COPM for each research site. The primary investigator will administer the COPM to obtain information that will be used to guide future interventions.

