## **Evaluation**

### **Data analysis**

The *R* software will be used for data analyses. Descriptive statistics will be used to analyze the demographic data, baseline information, and adherence with orthosis wearing. The linear mixed-effects model regression will be used as the omnibus test for examination of effect of intervention involving orthosis across time in comparison of that without. The

Orthosis for stroke  
Protocol Number: 1309M42881

systematic or fixed effects of this study are group assignment and time. Main effect of the two factors and the interaction effect between the two will be explored. Study participants will be considered and added into the model as the random effects.

General linear regression model will be used to determine effects of experimental conditions between the two groups. Data obtained from the pretest will first be used to examine if there are differences in outcome measures between the two groups. It will also serve as a covariate while examining difference between the two groups at the posttest 1. Data from the posttest 1 will serve as a covariate while examining difference between the two groups at the posttest 2. The *paired t* test will be used to examine difference within each group for each intervention period across time.

Interim monitoring of the data will occur after 16 participants complete the study. If the study results indicate a significant decline in functional performance for either group across the 12-week study, the study will be terminated. If there are serious adverse effects, the study would be terminated.

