### **Treatment Fidelity**

#### **Project personnel training**

**Interventionists.** The principle investigator, [name], serves as the primary interventionist. He will provide the Occupational Therapy Task-Oriented Approach (OTTO)

Orthosis for stroke  
Protocol Number: 1309M42881

based interventions for most participants throughout the study period. He will work closely and regularly with [name], the theorist behind the OTTO approach and the academic advisor, to ensure fidelity to the OTTO, monitor safety during the study period, and supervise the primary interventionist for the development and implementation of the OTTO based treatment plan.

The primary interventionist will develop treatment plans for all participants using the *Canadian Occupational Performance Measure*. The secondary investigator, [name], functions as a backup therapist when the primary interventionist is not available. He is a certified occupational therapist working at the Courage Kenny Research Institute and has participated in the previous clinical trial of OTTO.

Prior to data collection, the primary and the secondary investigators will discuss the concepts and procedures of OTTO based interventions. The primary interventionist will observe the backup therapist implementing the first one or two sessions for each study participant and discuss the content of treatment afterwards. The two will communicate via face-to-face and email discussions. If the secondary investigator becomes unavailable during the period of study, a third therapist will be sought and the same training procedure will be implemented.

**Blinded evaluator.** The blinded evaluators are occupational therapy students at University of Minnesota and University of Puget Sound. Each evaluator will conduct all evaluations for the same study participants, except the *Canadian Occupational Performance Measure*. The primary investigator will work with blinded evaluators on the implementation of the Wolf Motor Function Test, Motor Activity Log, ROM, and strength assessments. Inter-rater reliability: Prior to enrollment of the first participant,

Orthosis for stroke  
Protocol Number: 1309M42881

measurements between the primary investigator and the blinded evaluators will be within the standard error of measurement for each outcome measure prior to the enrollment of the first participant.

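### Two recruiting sites, but no site term in any model: a site difference in change adds noise and can shift the A–B estimate in a trial that happens to be imbalanced

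*Combined protocol and SAP*

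**What the plan says.** Under Participant selection, people are recruited from "local hospitals and institutions in the Twin Cities metro area" and from "the Onsite clinic at the University of Puget Sound". No number per site is given.

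Under Data collection plan and schedule, students from the two universities "will serve as the blinded evaluators to implement all assessments except the COPM for each research site". Project personnel training adds: "Each evaluator will conduct all evaluations for the same study participants", again except the COPM, which the primary investigator administers. The same section has one therapist treating most participants. A second "functions as a backup therapist when the primary interventionist is not available"; neither is assigned to a site.

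Treatment allocation sorts participants into mild, moderate and severe classes by Fugl-Meyer score and then says "Participants in each group will then be randomized in a 1:1 allocation ratio to either the Group A or B". Each class has ten envelopes, five for each arm. The text gives the envelopes no site dimension; the schematic (Figure 1) is not available to this review.

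Data analysis states that the "systematic or fixed effects of this study are group assignment and time", with their interaction, and participant as the random effect. The posttest 1 regression adds the pretest value, and the posttest 2 regression adds the posttest 1 value. No model mentions site.

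**The concern.** The 5:5 balance holds within each severity class over both sites together. Nothing holds it within a site, so one arm can by chance take a surplus of one site's participants. Setting and student evaluators differ between the sites, and case mix may differ too. With about 15 per arm, a surplus of a few people is a sizeable fraction of the arm.

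If participants at the two sites change by different amounts, two things follow. The unmodelled site difference stays in the residual and widens the interval. In a trial where site is imbalanced, part of that difference also appears as an orthosis effect. Sample size estimation says the results will be used to calculate effect sizes for a future study, so a chance shift could carry into its planning.

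**Working it through.** **Inputs from the documents.** 30 participants planned; three severity classes; ten envelopes per class, five A and five B; model terms as listed under Data analysis. Count check: 3 × (5 + 5) = 30, the planned enrolment, so no separate site set is described. The plan gives no alpha, power, effect size or SD to reproduce.

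**Assumed.** The number at the smaller site and its spread over classes; the size of a site effect; a pre–post correlation of 0.7; outcome SD 1; two-sided 5% tests.

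**1. Chance of site imbalance.** If a class has *m* smaller-site participants among its 10, the number *a* who go to Group A is hypergeometric: P(a) = C(m,a)·C(10−m,5−a)/C(10,5). The A–B count difference in that class is 2a − m, and the three classes add.

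Worked case, 6 participants as 2/2/2: in each class P(a=0) = P(a=2) = 56/252 = 0.2222 and P(a=1) = 140/252 = 0.5556. So P(|difference| ≥ 4) = 2 × [0.2222³ + 3 × 0.2222² × 0.5556] = 2 × [0.0110 + 0.0823] = 0.187.

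| At smaller site | Spread | P(difference ≥ 4) |
|---|---|---|
| 6 | 2/2/2 | 18.7% |
| 8 | 3/3/2 | 23.0% |
| 10 | 4/3/3 | 26.1% |
| 12 | 4/4/4 | 28.1% |

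With an odd number at the smaller site, only odd differences occur: P(difference ≥ 5) is 12% for 9 (3/3/3) and 16% for 15 (5/5/5). Clustering in few classes lowers the chance; 8 spread as 6/2/0 gives 14%.

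**2. What an imbalance carries into A–B.** A count difference of 4 is 4/15 = 0.267 of site share.

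- *Constant offset* (one site scores higher throughout). In the mixed model it cancels from group-by-time. In the regressions only (1 − slope) × 0.267 remains. For a 6:2 split, a 1 SD offset and correlation 0.7, the slope is about 0.75, leaving 0.25 × 0.267 = 0.067, or 7% of the offset. At correlations of 0.5 and 0.9 the figures are about 11% and 2%.
- *Difference in change.* The prior value does not absorb it, so about 27% passes through: 0.267 × 0.5, 0.8 or 1.0 SD = 0.13, 0.21 or 0.27 SD. The SE of a raw difference in means is √(2/15) = 0.365 SD; the SD of the baseline-adjusted estimate below is about 0.27.

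**3. With and without a site term.** Simulated posttest regression, 30 participants, 15 per site, 6,000 runs per row, no true A–B effect. Each pair is without/with site.

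| Site effect on change | Constant offset | SD of A–B | Rejection, all trials | Rejection, difference ≥ 5 |
|---|---|---|---|---|
| 0 | 0 | 0.266/0.273 | 0.048/0.049 | 0.041/0.040 |
| 0 | 1 SD | 0.265/0.267 | 0.050/0.046 | 0.062/0.047 |
| 0.5 SD | 0 | 0.283/0.273 | 0.054/0.050 | 0.106/0.055 |
| 0.8 SD | 0 | 0.307/0.270 | 0.049/0.048 | 0.115/0.047 |

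For an assumed true effect of 0.8 SD, the site term moves power from 0.72 to 0.81 if the site effect on change is 0.8 SD. If site has no effect, power moves from 0.82 to 0.81 and the SD from 0.267 to 0.272 (0.272/0.267 = 1.02).

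**4. Which term the mixed model needs.** A site main effect takes the same amount off every time point, so it leaves contrasts of change, and hence group-by-time, essentially as they were. Only site-by-time removes a site difference in change.

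**The case against.** The case for leaving the models alone is strong, and most of it stands.

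- Randomisation protects the comparison. A reader might infer that ignoring site biases the orthosis effect. It does not on average, and simulated type I error over all trials stays near 5%.
- A reader might also infer that 27% of any site difference in outcome enters A–B. That would hold for raw posttest means, which the plan does not compare. Under the planned models it applies only to a difference in change.
- Separate evaluators look like a confounder, but one evaluator per participant is what lets a constant offset cancel. Evaluators are trained to agreement (Data monitor) and must be within the standard error of measurement before first enrolment (Project personnel training). Site evaluators do not reach the COPM at all.
- Therapist differences might be thought to contaminate the orthosis effect throughout. Table 1 starts OTTO in week 9, after posttest 1, so OTTO delivery can matter only at posttest 2. The documents assign no therapist or calendar period to a site, so it cannot be said that the sites must differ in either.
- The trial is described as pilot work, and every site size and site effect used here is assumed.

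What survives is a possible site difference in change from setting, case mix, evaluator drift or, at posttest 2, OTTO delivery. Neither the allocation nor the models deal with it.

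**Conclusion.** The point holds as a cheap improvement, not as a threat to validity. The text shows two sites, balances allocation on severity alone and puts site in no model. The consequence is some lost precision, plus a shift in the particular trial that turns out imbalanced. With 6 to 12 of 30 at the smaller site, evenly spread over classes, a count difference of 4 or more has probability about 19% to 28%. Such a difference moves A–B by 0.13 to 0.27 SD if the site effect on change is 0.5 to 1.0 SD. If sites do not differ in change, little is lost by omitting the term. These sizes rest on the assumed site split, site effect and 0.7 correlation; the absence of a site term does not.

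**What to change.** Under Data analysis, add site (Minnesota or Puget Sound) as a fixed covariate in both posttest regressions. In the mixed model, add site and site-by-time. Site is already known for every participant.

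The cost is one degree of freedom in each regression. In the mixed model it is three fixed-effect parameters if the three time points are treated as categories (1 for site, 2 for site-by-time). If site does not affect change, the SD of the regression estimate rises by about 2%.

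Do not add small envelope blocks by site and severity. They would create 2 × 3 = 6 cells averaging 30/6 = 5 participants, and the primary investigator, who screens, assigns and also treats most participants, could then predict many assignments. That would trade a chance imbalance, which the model term can handle, for a risk of selection bias, which it cannot.
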